8.9. Scheduled Follow-up Visits

After receiving notice of a completed index ablation procedure, Medtronic will provide the target dates and windows for each visit to the site. Should a subject miss a visit or the visit fall outside the pre-specified window, a study deviation must be reported and the original follow-up schedule maintained for subsequent visits.

Data analyses include follow-up visits, regardless of whether the visit occurs within the window. Therefore, a late visit is preferred over a missed visit but must be accompanied by a deviation. Follow-up visit windows are listed in Table 8 and are based on days after the index ablation procedure.

Table 8: Follow-up Schedule

Occurrence/ Visit	Window (Calculated days after the ablation procedure)	
	Window Start	Window End
Enrollment/Baseline ¹	-30 days	Day 0
Index PFA System Ablation Procedure	Day 0	Day 0
30 day	30 days	44 days
3 month	91 days	105 days
6 month	183 days	197 days
12 month	365 days	395 days

¹Note: if the time between the consent date and the procedure exceeds 30 days, the subject must be re-evaluated against inclusion and exclusion criteria to ensure they still qualify for the study.

Multiple modes of data collections may be employed to support the collection of required visit data at the 3- and 6-month visits such as: In office patient clinic visit, direct to patient contact (i.e. telephone, email, mail contact, etc.), and remote technology transmissions/uploads.

The following information is required to be collected at the follow-up visits:

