8.19. Subject Withdrawal or Discontinuation (Subject Exit)

[figure not shown]
A subject can exit from the study at any time and is not obliged to provide a reason. If the subject wishes to exit early from the study, the site is required to document the reason, if available, for exit on an eCRF and in the subject's medical record. In addition, sites shall follow the regulations set forth by their IRB/REB/MEC. It is recommended that Investigators follow the subject until all device and/or procedure-related adverse events are recovered / resolved. For countries following ISO 14155:2011, permission may be requested to follow-up with the subject outside of the study based on problems related to the study device safety or performance. Following completion of the 12-month visit or early study exit, subjects will continue to receive standard medical care. All data available through the time of the subject's exit will be available for analysis.

Potential reasons for early study exit include:

- Subject lost to follow-up
- Subject did not meet inclusion/exclusion criteria after consent and did not undergo an ablation procedure
- The PFA system was not used during the subject's ablation procedure
- Subject did not provide proper consent or data use protection authorization
- Subject chooses to withdraw (e.g., consent withdrawal, relocation to another geographic location)
- Investigator deems withdrawal necessary (e.g., medically justified, failure of subject to maintain adequate study compliance)
- The sponsor decides the study will be closed or a particular site will be closed

In the case that the subject is determined to be lost to follow-up, details of a minimum of two attempts and the method of attempt (e.g., one letter and one phone record or two letters) to contact the subject must be recorded.

An unscheduled office visit should be attempted if the subject exits the study outside of a scheduled follow-up visit. Subjects treated with the PFA system who exit from the study should continue to be followed by an electrophysiologist for follow-up of any potential adverse events at the recommended interval of 12 months from the index PFA system ablation procedure.

9. Risks and Benefits

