Treatment success is defined as freedom from treatment failure. The study requires 24-hour Holter monitoring at 6 and 12 months in addition to weekly and symptomatic patient activated ambulatory monitoring transmissions from 3 through 12 months, and 12-lead ECGs at all follow up visits. Treatment failure is defined as any of the following components:

- Acute procedural failure (see definition below)
- Documented AF/AT/AFL on Holter/patient activated ambulatory/12-lead ECG after the 90-day post-ablation blanking period
- Minimum of 30 seconds on Holter/patient activated ambulatory or 10 seconds on 12-lead ECG recording
- Note: Documented occurrence and treatment of typical right-sided cavotricuspid isthmus dependent atrial flutter is not considered a failure.
- Any subsequent AF surgery or ablation in the left atrium, except for repeat PVI ablations using PFA within the 90-day blanking period.
- Direct current cardioversion for atrial tachyarrhythmia recurrences after the 90-day blanking period.
- Class I or III antiarrhythmic drug (AAD) dose increase from the historic maximum ineffective dose (prior to the ablation procedure) or initiation of a new Class I or III AAD after the 90-day blanking period. Note: remaining on the same pre-ablation dose or decreased dose of a previously failed or not tolerated Class I or III AAD after the 90-day blanking is not considered a failure.

Blanking period is defined as the first 90 days after the index ablation procedure. Recurrences of atrial arrhythmias during the blanking period will not be counted in the determination of the first clinical failure for the primary endpoint. Within the blanking period, recurrent arrhythmias can be managed with antiarrhythmic drugs or cardioversions. Titration of Class I and III antiarrhythmic medications are allowed during the blanking period.

Acute procedural failure is defined as:

- Inability to isolate all accessible targeted pulmonary veins (minimally assessed for entrance block and, where assessable, exit block) during the index procedure
- Ablation using a non-study device to isolate any pulmonary vein

Analysis Methods

The probability of a subject achieving effectiveness success at 12 months (365 days) will be estimated using survival analysis, the Kaplan-Meier method. The standard error will be approximated using Greenwood's formula. A two-sided 95% log-log confidence interval for the probability will be constructed.

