For every treated subject, day 0 is defined as the day of the index ablation procedure. For subjects with treatment failure, the survival date will be set to the date of the treatment failure. For subjects without treatment failure through 12 months, those subjects will be censored at the last study contact date recorded on a CRF which may include the last study visit, the last weekly patient activated ambulatory, the exit date, or death date. If a subject without a treatment failure is lost to follow-up, the censoring date will be set to the last known study visit date.

For the component of the endpoint, documented AF/AT/AFL, if this documentation resulted from rhythm monitoring occurring at the 12-month visit within the 12-month visit window, the date of recurrence will be set to 365 days from the study ablation procedure so that these events will be counted as treatment failures in the 12-month Kaplan-Meier analysis.

Sensitivity Analyses

A sensitivity analysis will be conducted to estimate the potential impact of subjects with less than 12 months of follow-up at the final analysis. The mortality rate in this patient population is anticipated to be low. The total assumed attrition rate through one year is 5%. Because the primary endpoint will be tested using survival methods, all treated subjects are included in the primary analysis, and therefore no subjects will have complete missing data. For subjects that exit early, a tipping point analysis will be conducted to estimate the potential impact of subjects with less than 12 months of follow-up. These subjects will be defined as subjects with partial data. The tipping point analysis methods will be as follows. For each subject with less than 12 months of follow-up, each subject will be set to treatment failure (failure date set to date of study exit). The 12-month Kaplan-Meier estimate will be re-calculated with the earliest (closest to index ablation) sequentially added to the Kaplan-Meier analysis, and the results presented in table format. The tipping point will be defined as the number of additional failures in which the performance goal (55% for paroxysmal and 40% for persistent) is crossed by the lower 95% confidence bound.

Performance Requirements

If the lower bound of the confidence interval (coverage level determined by the alpha spending function) is greater than the performance goal (55% for paroxysmal and 40% for persistent), the objective will be considered met.

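### The tipping-point analysis dates imputed failures at study exit with no cap at day 365, so a lost subject whose exit is recorded after day 365 escapes the stress test

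*Combined protocol and SAP*

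**What the plan says.** Section 12.2.3 reads the effectiveness result at a fixed time: "The probability of a subject achieving effectiveness success at 12 months (365 days) will be estimated using survival analysis", by Kaplan-Meier with a two-sided 95% log-log interval.

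Two dating rules apply to the same lost subject:

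- Primary analysis: "If a subject without a treatment failure is lost to follow-up, the censoring date will be set to the last known study visit date".
- Tipping point: "each subject will be set to treatment failure (failure date set to date of study exit", the parenthesis closing there with no upper limit on the date.

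The set to be imputed is described in two ways: "For subjects that exit early, a tipping point analysis will be conducted" and "For each subject with less than 12 months of follow-up". Neither says whether follow-up ends at the last visit or at exit. Imputation runs in order, "with the earliest (closest to index ablation) sequentially added to the Kaplan-Meier analysis".

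The Analysis Methods text just above moves a recurrence documented at the 12-month visit, within its window, to day 365 so that it counts. Imputed failures get no such adjustment.

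On exit timing, Table 8 closes the 6-month window on day 197 and opens the 12-month window on day 365, running to day 395. Under Section 8.9, if a visit is missed, "a study deviation must be reported and the original follow-up schedule maintained for subsequent visits". Section 8.19 requires "details of a minimum of two attempts and the method of attempt" before a subject is recorded as lost, but sets no deadline.

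**The concern.** A tipping-point analysis asks how many incomplete subjects would have to be failures before the conclusion changes. That works only if each imputed failure lands inside the estimate. A failure dated after day 365 does not. It also keeps the subject in the risk set through day 365, whereas the primary analysis removed that subject at the last visit. For such a subject the imputation can only hold or raise the estimate.

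This is the only sensitivity analysis for early exits visible in Section 12.2.3, in a single-arm trial judged against fixed goals (55% paroxysmal, 40% persistent). If some exits are recorded late, the analysis could report robustness that comes from the date on a form.

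**Working it through.** **Inputs from Section 12.2.3.** Arm sizes 165 and 150; assumed 12-month success 68% and 54%; assumed 6-month success 79% and 72%; 2% acute failure on day 1; chronic failures uniform on days 91–182 and 184–364; 5% attrition, uniform on days 1–364; Greenwood standard error, log-log interval.

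**Assumptions, because the documents give no figure.** The number lost (8 per arm in the worked case; 5% is 8.25 of 165 and 7.5 of 150), the last visit, and the share of exits dated after day 365, which is varied from 0 to 100%.

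**1. The plan's own figure.** Simulating these inputs with a single look at 95% gives power of 91.4% at 165 and 91.5% at 150, against the stated 90%. The alpha split is redacted, so exact agreement is not expected. The model is close enough to use.

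**2. Worked case.** Let *n* be treated, *a* failures by day 182, *d* failures by day 364, *L* = 8 lost and last seen on day 183, and *k* the number of those whose exit is dated after day 365.

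- Primary: S = (n−a)/n × (n−d−L)/(n−a−L)
- Tipping point, all 8 imputed: S = (n−d−L+k)/n

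Failure counts were set near the plan's rates: paroxysmal *a* = 33, *d* = 51; persistent *a* = 42, *d* = 68.

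| | Paroxysmal (lower bound) | Persistent (lower bound) |
|---|---|---|
| Primary | 132/165 × 106/124 = 68.4% (60.6%) | 108/150 × 74/100 = 53.3% (44.8%) |
| k = 0 | 106/165 = 64.2% (56.4%) | 74/150 = 49.3% (41.1%) |
| k = 4 | 110/165 = 66.7% (58.9%) | 78/150 = 52.0% (43.7%) |
| k = 6 | 112/165 = 67.9% (60.2%) | 80/150 = 53.3% (45.0%) |
| k = 7 | 113/165 = 68.5% (60.8%) | 81/150 = 54.0% (45.7%) |
| k = 8 | 114/165 = 69.1% (61.4%) | 82/150 = 54.7% (46.4%) |

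Each late exit removes one failure from the numerator. The stressed estimate passes the primary one at 7 of 8 late (paroxysmal) and at 6 of 8 late (persistent, 53.33% against 53.28%). Dating the failures at the censoring date gives the k = 0 row whatever the exit dates are.

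**3. Attrition spread over the year (5%).** Mean estimates by late share:

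| | Primary | 0% late | 50% late | 100% late | Break-even |
|---|---|---|---|---|---|
| Paroxysmal | 67.8% | 64.6% | 66.8% | 68.7% | about 75% |
| Persistent | 53.8% | 51.5% | 53.3% | 55.1% | about 60–65% |

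**4. Only dropouts after the 6-month visit exit late.** Paroxysmal: primary 67.90%, as written 66.56%, corrected 64.69%. The share of the intended fall that disappears is (66.56−64.69)/(67.90−64.69) = 1.87/3.21 = 58%. Persistent: 53.69%, 52.81%, 51.24%, so (52.81−51.24)/(53.69−51.24) = 1.57/2.45 = 64%. The stressed estimate exceeds the primary one in only 4% and 11% of simulated trials. Because the earliest are imputed first, the lowest row comes just before the late exits are added: 66.3% and 52.4%, slightly below the final row.

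**5. Tipping among trials that met the goal** (8 lost after month 6, all 8 imputed; ranges over separate simulation runs):

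| | Paroxysmal | Persistent |
|---|---|---|
| None late | 31–33% | 27–30% |
| Half late | 9% | 5–6% |
| All late | 0% | 0% |

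**6. The other reading.** If under 12 months of follow-up is counted to exit, subjects with late exits are never imputed and stay censored. Nothing rises, but they still go untested.

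**The case against.** The best defence is that late exits may be rare. The sample-size assumptions place all attrition on days 1–364, and the analysis is written for subjects who exit early. The schedule rule in 8.9 fixes the dates of later visits; it does not say that an unreachable subject stays enrolled until the 12-month window closes. From month 3 subjects transmit ECGs weekly, and Section 8.18 has the sponsor and core lab track compliance, so silence after month 6 could be noticed within weeks. Poor compliance is itself a listed reason for exit. The 5% is total attrition, so it includes deaths and withdrawals; a withdrawal whose exit is dated at last contact is unaffected, and 8 lost per arm is therefore towards the high end. The sensitivity analysis decides nothing formally, and Section 5.3 foresees a separate SAP that might settle the point.

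Much of this stands. A reader might infer that lost subjects are usually exited after day 365, or that the stress test as written raises the estimate and can never tip. The documents support neither: they give no exit timing, and both effects need most or all imputed exits to be late.

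It does not remove the defect. The assumed attrition timing is a planning input, not a rule for dating exits. Transmission tracking makes late recognition less likely but sets no deadline. The supplied text has no cap and no definition of follow-up length.

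**Conclusion.** The rule is wrong as written, with a consequence that depends on a quantity the documents do not give. Any lost subject whose exit is recorded after day 365 escapes the test. Such exits are possible because no visit is scheduled between days 197 and 365, the 12-month window runs to day 395, and declaring loss has no deadline.

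With no late exits the test behaves as intended. With half late it is much weakened. Its estimate exceeds the primary one only when roughly 60–75% or more of imputed exits are late (6 or 7 of 8 when all losses follow month 6), and tipping is excluded only when all are. These sizes rest on the plan's failure assumptions and on the assumed number and timing of losses. The primary test, success criterion and sample size are unaffected. It should be corrected before analysis.

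**What to change.** In the Sensitivity Analyses text of 12.2.3, replace the dating rule in the parenthesis with: failure date set to the subject's censoring date in the primary analysis, and no later than day 365. Define under 12 months of follow-up by that same censoring date, not by the date on the exit form.

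The cost is one sentence in the plan and one line of code. The stress test cannot become less strict, so the reported sensitivity result may be slightly less favourable. The primary analysis does not change.

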The PFA system is a novel catheter ablation technology, but analogous in procedural use to currently approved catheter ablation systems for the treatment of AF. The major complications related to traditional catheter ablation systems will describe the safety profile of the PFA system. The 2017 HRS/EHRA/ECAS Expert Consensus Statement on Catheter and Surgical Ablation of Atrial Fibrillation acknowledges that "AF ablation is an invasive procedure that entails risks, most of which are present during the acute procedural period. However, complications can also occur in the weeks or months following ablation." Symptoms and complications associated with AF ablation are stratified by those that occur within 1 month post-ablation and those that occur more than 1 month post-ablation.³ To evaluate the safety profile of the PFA system, the primary safety events in this study align with the recognized AF ablation complications. Recognizing that most AF ablation complications present acutely, Medtronic proposes that the safety profile of the PFA system will be established with 6-month follow-up data. The study will continue to collect, analyze and report all adverse events for all subjects through 12 months follow-up.

Sample Size Calculation

A sample size of 138 treated subjects followed for 6 months affords 90% power based on the following assumptions:

- 6-month safety rate = 5% (desired rate for new catheter ablation technology)
- OPC = 13% at 6 months
- Overall alpha = 0.025, one-sided
- One final analysis
- Binomial exact methods

The primary analysis will utilize Kaplan-Meier survival methods. Binomial exact methods were utilized for sample size and power calculations, as with very low expected attrition, Kaplan-Meier and binomial methods yield very similar results.

Determination of Subjects/Data for Analysis

All Primary Analysis Cohort subjects (only their index PFA procedure) will be included.

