CRYO4PERSISTENT AF Boveda S, et al. J Am Coll Cardiol. [Epub ahead of print]. ³⁰	prospective, single-arm, interventional post-market clinical study	11	101 cryo	ECG @ 3M, 6M, 12M and 48hr Holter @ 6M, 12M	AF/AFL/AT > 30s; Reablation	98.0%	81% (72-88)	61% (51-71)
1STOP Tondo C, et al. Heart Rhythm. 2017;15:363-368. ³¹	Prospective, single-arm	35	434 cryo	ECG and Holter @ 3M, 6M, 9M, 12M	AF > 30s; Reablation	98.5%	81% (77-84)	64% (59-69)
Aryana et al. Heart Rhythm. 2018;15:1121-1129. ³²	Consecutive, double-arm non-randomized	≤7	168 cryo (PVI only)	ECG @ 3M, 6M, 12M; 2-week TTM @ 6 weeks and 3-6 months	AF/AFL/AT > 30s	99.3%	67% (59-74)	47% (39-55)
STAR AF II Verma A, et al. N Engl J Med. 2015; 372: 1812-1822. ¹³	Prospective, triple-arm randomized,	48	67 RF (PVI only)	ECG and 24hr Holter @ 3M, 6M, 9M, 12M; Weekly and symptomatic TTM	AF > 30s; Reablation	97.0%	81% (70-90)	60% (47-72)
Weighted average (weights based on study sample size)							77.9%	59.5%

ⁱ Confidence interval calculated with binomial Fisher's exact method

ⁱⁱ 6-month effectiveness rates are estimated from survival curves published in literature, with the exception of the CRYO4PERSISTENT manuscript, which reported the 6-month effectiveness rate

Determination of Subjects/Data for Analysis

All Primary Analysis Cohort subjects will be included.

Sample Size Calculation

Given the separation of primary effectiveness objectives for paroxysmal AF and persistent AF, the study sample size is powered independently for paroxysmal AF and persistent AF arms.

For both arms, the sample size was computed using a simulation program. Given the assumptions below, the program ran through 10,000 simulations of this study for each potential sample size. The lowest sample size (going by units of 5 subjects) where at least 9000 studies were successful (i.e., power >90%) was chosen as the sample size for that arm.

The simulation program took into account the [REDACTED], alpha boundaries, the enrollment rate, and other assumptions listed below. Where percentages are assumed, it gave each simulated subject that chance of the event occurring (e.g., each simulated subject had a 2% chance of having an acute failure). It performed the primary effectiveness objective's analysis as stated above on each simulated study to determine whether that study would have been successful [REDACTED]

Assumptions (Paroxysmal Arm)

- The overall alpha will be 0.025, [REDACTED]
- Power=90%

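### The tipping point for primary effectiveness is defined at a fixed 95% bound, whereas the decision it tests uses a bound set by the alpha spending function

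*Combined protocol and SAP*

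**What the plan says.** All of the effectiveness wording is in section 12.2.3 of the combined protocol and SAP.

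- **Analysis Methods:** the 12-month success probability is estimated by Kaplan-Meier with Greenwood's standard error, and "A two-sided 95% log-log confidence interval for the probability will be constructed".
- **Sensitivity Analyses:** subjects with less than 12 months of follow-up are turned into failures at their exit date, earliest first, and the Kaplan-Meier estimate is recalculated at each step and tabulated. The tipping point is the number of added failures at which the performance goal "55% for paroxysmal and 40% for persistent) is crossed by the lower 95% confidence bound".
- **Performance Requirements**, the next paragraph: "If the lower bound of the confidence interval (coverage level determined by the alpha spending function) is greater than the performance goal", the objective is met.
- **Sample Size Calculation:** in each arm, "The overall alpha will be 0.025"; the text that follows is redacted. The simulation took into account "alpha boundaries, the enrollment rate, and other assumptions listed below".

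The primary safety objective (12.2.2) does not have this mismatch. It assumes "One final analysis" and decides on the same two-sided 95% interval that it constructs.

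**The concern.** A tipping-point analysis should show how many unfavourable outcomes among early exits would reverse the primary conclusion. It does so only if it uses the bound that decides the conclusion. Here adjacent paragraphs use two different levels, and no visible sentence links them.

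The direction of any discrepancy is known. Spending part of the 0.025 before the final analysis lowers the final one-sided level and widens the deciding interval. A count against the 95% bound is then either the same as the correct one or too favourable.

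The plan assumes 5% attrition, about 8 subjects per arm (0.05 × 165 = 8.25; 0.05 × 150 = 7.5). The tipping table will therefore have few steps, and one or two failures are a visible part of it.

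**Working it through.** **Inputs.** From 12.2.3: goals of 55% and 40%, 165 and 150 subjects, overall alpha 0.025 (taken as one-sided, to match the one-sided alternative), log-log interval with Greenwood standard error. The final-analysis level is redacted, so 0.025 down to 0.015 is an assumed range.

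**Reproducing the plan's own figure.** A single-look simulation on the plan's assumptions (2% acute failure, 6- and 12-month rates of 79% and 68% or 72% and 54%, 5% uniform attrition; 10,000 trials per size) at one-sided 0.025 gave power of 91.6% with 165 paroxysmal subjects and 90.8% with 150 persistent subjects. Both are within 2 points of the stated 90%.

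**Formula.** With no censoring, s successes in n give S = s/n, and the standard error of log(−log S) is

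se = √[(1 − S)/(nS)] / |ln S|,

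so the lower bound at one-sided level a is L = S^exp(z₁₋ₐ × se).

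**Boundary cases.**

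- Paroxysmal, 104/165: S = 0.6303, se = 0.1292. At 0.025 (z = 1.960), L = 0.6303^1.288 = 55.18%, so the goal is not crossed. At 0.022 (z = 2.014), L = 0.6303^1.297 = 54.95%, so it is. The switch is at 0.0226.
- Persistent, 73/150: S = 0.4867, se = 0.1164. At 0.025, L = 0.4867^1.256 = 40.46%. At 0.0175 (z = 2.108), L = 0.4867^1.278 = 39.83%. The switch is at 0.0193.

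**Minimum successes (maximum failures) that still meet the goal.**

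| One-sided level | Two-sided coverage | Paroxysmal, n = 165 | Persistent, n = 150 |
|---|---|---|---|
| 0.025 | 95.0% | 104 (61) | 73 (77) |
| 0.022 | 95.6% | 105 (60) | 73 (77) |
| 0.020 | 96.0% | 105 (60) | 73 (77) |
| 0.0175 | 96.5% | 105 (60) | 74 (76) |
| 0.015 | 97.0% | 106 (59) | 74 (76) |

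Against the first row, the fixed 95% rule tolerates 0 to 2 failures too many in the paroxysmal arm and 0 to 1 in the persistent arm.

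**What spending might leave (illustration, two looks assumed).** O'Brien-Fleming-type spending of 0.025 with the first look at information 0.5, 0.7, 0.8 or 0.9 leaves 0.0245, 0.0228, 0.0214 or 0.0200. The first two are above both switch points, so nothing changes. The last two cost one failure in the paroxysmal arm and none in the persistent arm. Pocock-type spending (first look at 0.3 to 0.9) leaves 0.0119 to 0.0169. At 0.0119 (z = 2.260), 106/165 still gives 0.6424^exp(2.260 × 0.1312) = 55.1%. In the persistent arm 74/150 fails below 0.0132, but 75/150 gives 0.5^exp(2.260 × 0.1178) = 40.5%. The gap is still at most 2 in each arm.

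**The tipping procedure itself, with censoring.** Simulated on the plan's assumptions with one look, as a share of trials that met the goal at the assumed final level:

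| Assumed level | Tips later at 95%: paroxysmal / persistent | Tips at the deciding level but never at 95%: paroxysmal / persistent |
|---|---|---|
| 0.0245 | 2% / 1% | 0% / 0% |
| 0.022 | 23% / 6% | 6% / 0% |
| 0.0147 | 33% / 18% | 13% / 6% |

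**The case against.** The strongest reply is that this changes little. Performance Requirements is explicit and is the only success criterion. Nothing visible makes success depend on the tipping point, and the results of the sequential steps are tabulated, so a reader could apply another bound. The alpha split is redacted, and the redacted text may state the final coverage or how the two intervals relate. All of that stands. It limits the size and weight of the point, but the visible tipping-point definition still names a level other than the one that decides.

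Three stronger readings are tempting, and the documents do not support them.

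- *The sample sizes prove that the final level is below 0.025.* The plan's rule is "The lowest sample size (going by units of 5 subjects) where at least 9000 studies were successful (i.e., power >90%) was chosen". In a one-look simulation at 0.025 the smallest such sizes were 160 (90.5%) and 145 (90.2%), one step below the stated 165 and 150. But another run gave 90.0% at 160. With 10,000 runs the Monte Carlo standard error near 90% is √(0.9 × 0.1/10,000) = 0.3 points, and a one-look model leaves out the redacted looks. The stated sizes are compatible with a lower final level but do not establish one.
- *The two-sided 95% interval is an error.* A nominal 95% interval reported beside a spending-adjusted decision is ordinary practice. It only needs to be identified as descriptive where it differs from the deciding interval.
- *The tipping bound is a one-sided 95% bound, level 0.05.* That would lower the required successes to 102 and 71. However, the only interval defined for this endpoint is two-sided 95%, so its lower limit is the natural meaning.

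**Conclusion.** The mismatch is real and can be seen without the redacted text: the decision uses the "coverage level determined by the alpha spending function", and the tipping point uses a fixed 95%. Its effect is conditional. If the final coverage is exactly 95%, only the wording is inconsistent. If any alpha is spent earlier, the stated tipping point can come too late, by 0 to 2 failures over the assumed levels of 0.025 to 0.015. The counts assume no censoring, and the simulated frequencies assume one look.

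A reader might infer that the primary conclusion is at risk, or that the plan will declare a lost result robust. Neither follows: the tipping analysis is supportive, and the success rule stands apart from it. Severity: minor.

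**What to change.** In 12.2.3, Sensitivity Analyses, end the tipping-point definition with: *the lower log-log confidence bound at the coverage level the alpha spending function assigns to the analysis at which the primary effectiveness decision is made.* In Analysis Methods, add that the two-sided 95% interval is descriptive wherever its coverage differs from that of the deciding interval.

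The plan places the tipping analysis at the final analysis, so the authors should also confirm that this wording gives the level they intend if success has been declared at an earlier look.

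The cost is one replaced phrase, a short note and one program parameter. The tipping count may stay the same or become slightly less favourable. Sample size, power and the primary test do not change.

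### The effectiveness tipping point is measured against a fixed 95% bound, although success is decided at the alpha-spending level (minor)

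*Combined protocol and SAP*

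**What the plan says.** All the relevant text is in section 12.2.3 (Primary Effectiveness Objective).

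- **Analysis Methods:** "A two-sided 95% log-log confidence interval for the probability will be constructed", from Kaplan-Meier at 365 days with Greenwood's standard error.
- **Performance Requirements:** the objective is met "If the lower bound of the confidence interval (coverage level determined by the alpha spending function) is greater than the performance goal", which is 55% in the paroxysmal arm and 40% in the persistent arm.
- **Sensitivity Analyses:** the purpose is to "estimate the potential impact of subjects with less than 12 months of follow-up at the final analysis". Early exits are set to failure at their exit date, "with the earliest (closest to index ablation) sequentially added", and the results are tabulated. The tipping point is the number of added failures at which the goal "is crossed by the lower 95% confidence bound".
- **Sample Size Calculation:** "The overall alpha will be 0.025" in each arm, with the rest of the line redacted. The simulation is said to have used alpha boundaries, in the plural. Their values and the look schedule (12.2.1) are redacted.

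The safety objective (12.2.2) differs. It lists a single final analysis and names the 95% interval in its own success rule.

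**The concern.** A tipping-point analysis should count the missing-outcome failures needed to overturn the conclusion that was declared. That works only if the bound being watched is the bound that decided success. Here the decision is made at the spending level and the tipping count at 95%. If alpha is spent at an earlier look, the final interval is wider than 95%. The 95% bound then lies above the deciding bound and crosses the goal later, or at the same step. Any discrepancy therefore makes the result look more robust than it is.

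Two further features of the definition matter. It does not say whether the 95% bound is one-sided or two-sided, and a one-sided reading would widen the gap. The prescribed earliest-first order is also the gentler of the two natural orders.

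**Working it through.** **1. Reproducing the plan's own figures.** The inputs are those of 12.2.3:

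- 12-month success of 68% (paroxysmal) and 54% (persistent), and 6-month success of 79% and 72%;
- 2% acute failures on day 1;
- chronic failures uniform over days 91–182 and 184–364;
- 5% uniform attrition.

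Simulated trials were tested with the Kaplan-Meier log-log lower bound at a fixed one-sided 0.025, without modelling the redacted looks. Power was 91.2% at N=165 and 91.6% at N=150, against the stated 90%. Type I error was 2.1% in both arms. The smallest N reaching 90% was 160 and 145 at 0.025, and 165 and 150 at a final level of about 0.022–0.023. The stated sizes therefore fit a final level slightly below 0.025, but this is only suggestive.

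**2. Plausible final levels (assumed).** With overall one-sided alpha of 0.025 and one interim look at 50% to 90% information:

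- O'Brien-Fleming-type spending leaves 0.0245 to 0.0200 (two-sided coverage 95.1% to 96.0%).
- Pocock-type spending leaves about 0.0139 to 0.0119 (97.2% to 97.6%).

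The level 0.0147 (97.1%) serves as a further illustrative value.

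**3. Thresholds with complete data.** With no censoring, S = s/n and the Greenwood term is V = (1 − S)/(nS). The lower bound is exp{−exp[ln(−ln S) + z√V/|ln S|]}.

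Example: s = 104, n = 165. S = 0.6303, |ln S| = 0.4615, √V = √(0.3697/104) = 0.0596, and √V/|ln S| = 0.129. With z = 1.960 the bound is 0.552, above 0.55. With z = 2.178 (level 0.0147) it is 0.543, below 0.55.

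Minimum successes needed:

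| Final one-sided level | Paroxysmal (n=165, goal 55%) | Persistent (n=150, goal 40%) |
|---|---|---|
| 0.025 | 104 | 73 |
| 0.0245 | 104 | 73 |
| 0.0225 | 105 | 73 |
| 0.020 | 105 | 73 |
| 0.0147 | 106 | 74 |

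The allowance for failures falls by 0 to 1 (paroxysmal) and 0 (persistent) for levels from 0.0245 to 0.020, and by 2 and 1 at 0.0147. At 0.0125 the persistent requirement is 75, a fall of 2.

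**4. Number of partial-data subjects.** Attrition of 5% gives 0.05 × 165 = 8.25 and 0.05 × 150 = 7.5 exits. Some of these follow a failure already counted. Simulation leaves about 6.9 and 5.7 event-free early exits.

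**5. How often the tipping count changes.** The plan's procedure was run on 6,000 simulated trials per arm at the design rates. Percentages are of all simulated trials:

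| | Paroxysmal | Persistent |
|---|---|---|
| Passes both bounds, count differs: O'Brien-Fleming type | about 2%–25% | about 1%–11% |
| Passes both bounds, count differs: Pocock type | 28%–30% | 15%–20% |
| Never tips at 95% but tips at the deciding bound: O'Brien-Fleming type | 0%–6% | 0% |
| Never tips at 95% but tips at the deciding bound: Pocock type | 12% | 6%–11% |

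**6. Order of conversion.** Converting an exit with r subjects at risk multiplies the 12-month estimate by (1 − 1/r). An early exit has r ≈ n, so the drop is about S/n: 0.68/165 = 0.0041 and 0.54/150 = 0.0036. A late exit has r ≈ nS, so the drop is about 1/n: 0.0061 and 0.0067. In simulation at the design rates and the 95% bound, latest-first tipped sooner in about 20% of paroxysmal wins and about 10% of persistent wins, usually by one subject. It never tipped later.

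**The case against.** The strongest reply is that the plan has one decision rule and it is clear. Performance Requirements alone decides success, at the spending level. The interval in Analysis Methods is estimation, and a 95% interval beside a group-sequential test is ordinary reporting. This stands. A reader might infer that two incompatible bounds compete for the primary decision, or that type I error is inflated. Overall one-sided alpha would be about 2.5% to 3.4% if a 95% bound decided the final analysis after one interim look. The documents do not support that inference: the decision rule excludes the 95% bound, and the plan reports simulated overall alpha below 2.5%.

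A second reply is that the boundaries are redacted, so the gap cannot be sized and might be zero. That is correct about size. If no alpha is spent early, the two-sided 95% bound and the deciding bound coincide. Redaction does not remove the mismatch in wording, because both sentences are visible and neither refers to the other.

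A third reply is that the conversion order is pre-specified and the full sequence is tabulated. The last row, with every early exit set to failure, is the same in any order, so a result that survives it is robust regardless. In simulation about three quarters of paroxysmal wins and 84% of persistent wins never tipped in either order. This also stands, and it makes the order a matter of completeness. It does not change the fact that the single headline count comes from the gentler order.

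**Conclusion.** The point holds as a minor inconsistency. If any alpha is spent before the final analysis, the tipping count can match or overstate the number of added failures that would reverse the conclusion, and can never understate it. This assumes the 95% bound means the lower limit of the two-sided interval; a one-sided 95% bound would make the gap larger.

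The size rests on assumed final levels: 0 to 1 subject (paroxysmal) and 0 (persistent) under O'Brien-Fleming-type spending, and 2 and 1 at 0.0147, against about 7 and 6 partial-data subjects. A reader might take two subjects as the general figure. It needs Pocock-like spending, and the stated sample sizes fit a final level nearer 0.022–0.023, where the gap is at most one subject in the paroxysmal arm and none in the persistent arm. The primary test, its type I error and both sample sizes are unaffected.

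**What to change.** In the tipping-point definition, replace the 95% bound with: *the lower bound of the two-sided log-log confidence interval at the coverage level the alpha spending function assigns to the final analysis*. Tie it to the final analysis, not to whichever look declares success, because the sensitivity analysis is run on final data and an interim boundary would not fit it. The 95% interval in Analysis Methods can stay, ideally labelled as descriptive.

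Add one column to the tipping table with exits converted latest-first, beside the planned earliest-first column.

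The cost is one wording change and one table column, with no new data. The reported tipping count may be slightly less favourable.
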